Academy of Neurology to be the first-line intervention for tics.⁶ Immediately prior to each CBIT session, participants will undergo TMS targeting the SMA. The specific type of TMS procedure will be randomly assigned between subjects and be either: 1 Hz repetitive TMS (rTMS), continuous theta burst stimulation (cTBS), or sham stimulation.

4.2. Drug/Device Handling:

TMS device. Stimulation will be delivered using a Magstim Super Rapid2 stimulator (Magstim Company Ltd, UK). The device will be used to deliver electromagnetic stimulation through a small coil positioned over a targeted area on the scalp. The manufacturer's indication for use is to stimulate peripheral nerves and the human cortex for diagnostic and research purposes.

We will use a Magstim air-cooled 70mm figure-eight coil for motor threshold determination and active TMS conditions. Sham stimulation will use the Magstim sham air-cooled coil, which produces auditory signals identical to an active coil but contains a mu-metal shield that diverts the majority of the magnetic flux such that a minimal (<3%) magnetic field is delivered to the cortex.

The device is installed and set-up at the University of Minnesota Non-Invasive Neuromodulation Laboratory (NINL). The device will only be able to be administered by trained personnel. The device is located in a locked, access controlled room.

[figure not shown]
Operation of the TMS device (MAGSTIM Super Rapid 2) will follow the procedures outlined in the attached "Operating Manual."

- 4.3. Biosafety: N/A
- 4.4. Stem Cells: N/A
- 4.5. Fetal Tissue: N/A

5. Procedures Involved

5.1. **Study Design**: The study is a double-blinded randomized control trial that will examine whether combining Comprehensive Behavioral Intervention for Tics (CBIT) with inhibition of the

PROTOCOL TITLE: Transcranial Magnetic Stimulation to Augment Behavior Therapy for Tics VERSION DATE: 2/24/2022

supplementary motor area (SMA) using transcranial magnetic stimulation (TMS) normalizes activity in the SMA-connected circuits, improves tic suppression ability, and enhances CBIT outcomes in young people with tic disorder. We will compare two rTMS procedures, 1 Hz rTMS and continuous theta burst stimulation (cTBS), against sham stimulation. Youth with chronic tics (n = 60) will complete 10 daily sessions of CBIT plus randomly assigned TMS procedure, with fMRI, behavioral, and clinical assessments before and after treatment and at 1 and 3 month follow-ups (figure 1).

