• Aim 1. Target engagement: Brain. 1) Primary measure of neural target engagement will be decreased activation in SMA. Hypothesis 1: Either or both active TMS groups will demonstrate within-subject decrease (effect size $\eta 2=0.18$ in an ANOVA) in SMA activation post-treatment, as measured with an fMRI finger tapping task. While this is a large effect size in practice, we point out that Wu et al (2014) observed a much larger effect size of η 2=0.41 in the decrease in SMA activity comparing active vs sham cTBS. 2) Secondary measure of neural target engagement will be change in fMRI resting state functional connectivity of at least one SMA-mediated circuit (SMA-DLS, SMA-M1). Hypothesis 2: Either or both active TMS groups will demonstrate within-subject change (effect size $\eta 2=0.18$ in an ANOVA) in resting state fMRI connectivity (RSFC) of at least one SMA-mediated circuit (SMA-DLS, SMA-M1) post-treatment. A region of interest (ROI) analysis will be performed to determine the time*treatment group differences in SMA activation elicited by an fMRI motor task (finger tapping). The SMA ROI will be identified by placing a seed (sphere with 5mm radius) that matches the coordinate used for individual TMS coil placement. Activation parameters in the SMA will be identified in a first-level analysis, using a general linear model (GLM) to model each subject's SMA time course during the motor task. These activation parameters will be used in a subsequent linear mixed effects (LME) model. The predictors of the LME will include the baseline activation, group indicators for

PROTOCOL TITLE: Transcranial Magnetic Stimulation to Augment Behavior Therapy for Tics VERSION DATE: 2/24/2022

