the stimulation groups, and baseline x group interactions. Random effects will be used to model within-subject variation from the first-level analyses. Altogether, the LME will allow us to model how the within-subject change in activation from pre-treatment to post-treatment differs across active and sham conditions. *In addition*, we will also investigate the effects of each TMS regimen on the connectivity in the entire CSTC. To this end, we will extract the ROI-level time courses from each region in the CSTC, and we will use partial correlations to obtain an estimate of connectivity between each ROI pair within the CSTC while accounting for the data observed in the other ROIs. Given the collection of partial correlations for each study participant, we will use the SPU test, which uses the collection of partial correlations simultaneously, to assess for group differences across the sham and TMS regimens.⁷⁵

- Aim 2. Target engagement: Behavior. Hypothesis: Either or both active TMS groups will show within-subject improvement (small effect size of at least Cohen's d = 0.3) in tic suppression ability as measured by the Tic Suppression Task (TST). TST "tic suppression ability" scores will serve as the primary outcome in an ANOVA model. An ANOVA will be used to establish if there exist differences in how the 1Hz, cTBS, and sham conditions affect change in tic suppression ability from pre- to post-treatment. Group indicators for these conditions will be the primary predictors for the model.
- Aim 3. Assess dose-response relationship. Changes in brain (Aim 1) and behavior (Aim 2) targets will be compared between active TMS groups (1Hz rTMS vs. cTBS) using ANOVA. In the case that both active TMS regimens are found superior to sham, we will compare the regimens on safety and feasibility. We will use 2-sample t-tests to compare the two regimens using data from our safety and feasibility measures and prioritize the regimen with significantly better (p<.05) outcomes.
- 15.2. Power Analysis: In Aim 1, hypothesis 1 our proposed sample size after accounting for expected attrition will give us 80% power to detect an effect size of at least $\eta^2=0.18$ for differences in SMA activation between active TMS and sham. For Aim 2, our proposed sample size will give us 80% power to detect an effect size of at least d = 0.90 for a within-subject improvement in tic suppression ability. Our preliminary data showed effect sizes of this magnitude.

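### The Aim 1 SMA-activation model contains baseline-by-group interactions but does not say at which baseline the arms are compared or which contrast tests Hypothesis 1, and the stated 80% power is not tied to this model

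*Combined protocol and SAP*

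**What the plan says.** Section 15.1, Aim 1, announces the purpose of the analysis: "A region of interest (ROI) analysis will be performed to determine the time*treatment group differences in SMA activation". First-level activation estimates then go into a linear mixed effects model. "The predictors of the LME will include the baseline activation, group indicators for" "the stimulation groups, and baseline x group interactions". The same paragraph says random effects represent within-subject variation from the first-level analyses, and that the model addresses how pre-to-post change differs between active and sham conditions.

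The section does not state the response variable (post-treatment value, change, or both scans), whether baseline is centred, or which coefficient or contrast decides Hypothesis 1.

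On size, section 15.1 gives the target as "effect size $\eta 2=0.18$ in an ANOVA". Section 15.2 says "our proposed sample size after accounting for expected attrition will give us 80% power to detect an effect size of at least" 0.18 "for differences in SMA activation between active TMS and sham". Attrition, allocation ratio and the Aim 1 significance level are not given. Section 5.1 sets the planned number: "Youth with chronic tics (n = 60) will complete 10 daily sessions of CBIT". Aim 3 compares brain changes between the two active arms by ANOVA, with no mention of baseline adjustment.

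Section 15.1 makes SMA activation the primary neural measure, whereas section 3.1 names resting-state connectivity as the primary neural endpoint. Here, primary follows section 15.1 only.

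**The concern.** With indicator coding and a baseline-by-group interaction, each group coefficient is the active-minus-sham difference for a participant whose baseline equals zero on the scale entered. If baseline is centred, that participant is average. If baseline is raw, it is someone with no SMA activation. Few participants are likely to be there: section 5.2 chooses the coil target for high finger-tapping activation, and section 15.1 places the ROI at that coordinate.

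The listed model therefore supports several tests of Hypothesis 1 that differ in meaning and power, and nothing fixes the choice before the data are seen. An unfavourable choice could miss real target engagement. The result also feeds Aim 3, where the safety and feasibility comparison starts only if both active regimens beat sham.

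**Working it through.** **Inputs from the documents.** Eta-squared 0.18, power 80%, planned N = 60, three arms.

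**Assumptions, because the documents are silent.** 1:1:1 allocation; alpha 0.05; pre-post correlation 0.5; both active arms shifted equally; baseline mean/SD between 1 and 3. Completers are taken as 48 (20% attrition).

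**1. Reproduce the stated power.** For a one-way three-group ANOVA, f² = 0.18/0.82 = 0.2195 (f = 0.469), the noncentrality is f² × N, and the degrees of freedom are (2, N − 3).

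| N | Noncentrality | Power |
|---|---|---|
| 60 | 13.17 | 89.6% |
| 54 | 11.85 | 85.8% |
| 48 | 10.54 | 80.9% |
| 47 | 10.32 | 80.0% |
| 46 | 10.10 | 79.0% |

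So 80% corresponds to an ANOVA with about 46-48 completers. This is not the only possible source: a two-group comparison with 40 participants in total gives 82%. Either way, the calculation has no baseline term and no interaction.

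**2. Convert the effect.** With arm effects (0, 1, 1), the variance of the pattern is 2/9. The shift giving f² = 0.2195 is √(0.2195/0.2222) = 0.99 residual SD.

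**3. What raw coding does.** When baseline is uncentred, the standard error of each group coefficient grows by about √(1 + (mean/SD)²):

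- ratio 1: √2 = 1.4
- ratio 2: √5 = 2.2
- ratio 3: √10 = 3.2

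The noncentrality shrinks by the square of these factors: 10.54/2 = 5.27, 10.54/5 = 2.11 and 10.54/10 = 1.05. With (2, 42) df, this large-sample approximation gives 50%, 22% and 13%.

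**4. Simulated power at N = 48, effect constant across baseline.**

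| Test | Power |
|---|---|
| 2-df group test, no interaction | 79-81% |
| 2-df group test at mean baseline, interaction kept | 78-80% |
| Joint 4-df test of group and interaction | 67-69% |
| 2-df test of raw group terms, mean/SD = 1 | 47% |
| 2-df test of raw group terms, mean/SD = 2 | 20% |
| 2-df test of raw group terms, mean/SD = 3 | 12-13% |

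With all 60 analysed, the raw-term figures are 58%, 26% and 15%, against 88% at mean baseline and 81% for the joint test. Type I error stays near 5% throughout, so the issue is power and meaning, not false positives.

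**5. Effect proportional to baseline, same average size, N = 48, mean/SD 1 to 3.** The raw group terms reject about 5% of the time, because by construction there is no effect at zero. The mean-baseline test with the interaction kept has 77-79%. The no-interaction model has 70%, 76-77% and 79%.

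**6. Aim 3.** Residual variance is proportional to 2(1 − ρ) for a change score and to 1 − ρ² after baseline adjustment. The ratio is (1 + ρ)/2, or 0.75 at ρ = 0.5. Baseline adjustment uses data already collected and removes about a quarter of the variance.

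**The case against.** The strongest reply is that the plan states its target, the difference between conditions in pre-to-post change. A group contrast at mean baseline, taken from the listed model, estimates that whether or not baseline is centred, and it keeps about 78-80% power. On that reading nothing is lost. This stands. A reader might infer that the plan tests the TMS effect at zero activation, or leaves baseline uncentred. The documents support neither: they are silent on coding, and the predictor list is introduced as what the model will include, so it need not be complete.

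Three further inferences also fail.

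- **Missing time term.** It is not an error in itself. In a baseline-adjusted model of the post-treatment value, the arm difference is also the adjusted difference in change.
- **Random effects.** The text says they represent first-level variation, so it does not follow that a subject effect has been misplaced and must be dropped.
- **The interaction as a fault.** With a mean-baseline contrast it costs almost no power, and when the effect grows with baseline, keeping it does as well or better.

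What the reply does not supply is the choice itself. Several analyses fit the text, and the power statement does not say which one it describes.

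**Conclusion.** The point holds as a gap in the definition of a key test. Section 15.1 lists a model whose group indicators do not by themselves measure the average effect, and it does not name the response, the baseline level or the contrast. Section 15.2 expresses power for an ANOVA. At 48 completers, the analyses compatible with the text range from about 12% power (raw group terms, mean/SD of 3) through about 67-68% (joint 4-df test) to about 78-81% (arms compared at mean baseline).

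The low figures apply only if raw baseline is used and the group terms are tested. They also rest on an assumed mean/SD ratio, attrition, allocation ratio and pre-post correlation. The documents do not show that the 80% is wrong. They leave open whether it belongs to the test that will be run.

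**What to change.** In section 15.1:

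- Define the Aim 1 SMA-activation analysis as post-treatment activation regressed on mean-centred baseline activation and arm.
- Name the active-minus-sham contrasts at mean baseline, with 95% confidence intervals, as the test of Hypothesis 1.
- Make baseline-by-group exploratory. Alternatively, keep it in the model with centred baseline and the same contrasts.
- Take the Aim 3 comparison of 1 Hz with cTBS on the brain outcome from this baseline-adjusted model instead of an ANOVA on changes.

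In section 15.2, state the power for the named test, with the attrition, allocation ratio and alpha it assumes.

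The cost is SAP wording; no new data are needed. The downside is that if the interaction becomes exploratory, whether the effect varies with baseline activation becomes a secondary question.

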stimulation (cTBS) did not find group-level clinically meaningful change, although an extended dose (total of 6 weeks daily) did improve outcomes with 1Hz.³⁶ Importantly, in the only study measuring neural correlates of treatment, Wu et al.³³ detected significant decreases in activation of SMA and functionally connected CSTC nodes (i.e., bilateral M1) after only a 2 day course of cTBS, leading to continued interest in using TMS to alter tic-related neural pathology.

Our recent research suggests rTMS improves tic suppression ability more robustly than it reduces baseline tic frequencies. PI [name] measured acute effects of 1 Hz vs. sham rTMS over SMA using the TST (K23MH103617; for detail see "Preliminary Data" below) and found that active 1Hz rTMS enhances tic suppression ability. Notably, reduction in tic frequency was more robust in conditions measuring tic suppression ability compared to a "free to tic" baseline. These data suggest that inhibitory stimulation of SMA with rTMS may benefit those with tics by enhancing their capacity to voluntarily inhibit tics.

2.3. Existing Literature: Taken together, the existing literature and our preliminary data suggest that augmenting CBIT with inhibitory stimulation of SMA using TMS may boost tic suppression ability, which in turn may increase the efficacy of CBIT. This synergistic approach aligns with converging evidence suggesting that combining brain stimulation with targeted therapy is a potentially powerful approach for treating neuropsychiatric disorders.³⁷

3. Study Endpoints/Events/Outcomes

- 3.1. Primary Endpoint/Event/Outcome:
 - 1) Neural target engagement: Within-subject change in resting state fMRI connectivity of SMA-mediated brain circuits.
 - 2) Behavioral target engagement: Within subject change in tic suppression ability as measured by the Tic Suppression Task (TST).
- 3.2. Secondary Endpoint(s)/Event(s)/Outcome(s):
 - 1) Two TMS procedures, both intended to inhibit activity in SMA, will be compared using data from our safety and feasibility measures.
 - 2) Between group differences on secondary measures of clinical and neural function.

4. Study Intervention(s)/Investigational Agent(s)

4.1. Description: All participants will receive 10 daily sessions of CBIT, a wellestablished behavioral treatment that is considered by the American

PROTOCOL TITLE: Transcranial Magnetic Stimulation to Augment Behavior Therapy for Tics VERSION DATE: 2/24/2022

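### The Aim 2 hypothesis (d = 0.3) and power sentence (d = 0.90) are worded as within-subject improvement, but the planned test compares change across 1 Hz, cTBS and sham

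*Combined protocol and SAP*

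**What the plan says.** **Aim 2 hypothesis (section 15.1).** "Either or both active TMS groups will show within-subject improvement (small effect size of at least Cohen's d = 0.3) in tic suppression ability". Sham is not mentioned.

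**Aim 2 planned test (section 15.1).** An ANOVA is to establish whether there are "differences in how the 1Hz, cTBS, and sham conditions affect change in tic suppression ability" from before to after treatment, with group indicators as the main predictors.

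**Aim 2 power (section 15.2).** The sample size is said to give "80% power to detect an effect size of at least d = 0.90 for a within-subject improvement in tic suppression ability". This sentence does not mention attrition, a comparator, or the SD that scales d.

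**Aim 1 power (section 15.2), for contrast.** Here "our proposed sample size after accounting for expected attrition will give us 80% power" at an eta-squared of 0.18, for "differences in SMA activation between active TMS and sham". Attrition and comparator are both named.

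**Design.** Section 5.1: "We will compare two rTMS procedures, 1 Hz rTMS and continuous theta burst stimulation (cTBS), against sham stimulation". Aim 3 opens one of its comparisons with "In the case that both active TMS regimens are found superior to sham". Section 4.1 gives CBIT to all participants, and section 2.1 describes stronger voluntary tic suppression as the central aim of CBIT.

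**Hypothesis 2 (section 15.1, Aim 1).** Success is a change in at least one of two circuits (SMA-DLS, SMA-M1) in either or both active arms. No error control is stated. Connectivity is called the secondary neural measure here, but section 3.1 lists it as a primary endpoint.

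**The concern.** The trial asks what TMS adds to CBIT. A within-subject gain in an active arm cannot answer that, because CBIT, practice on the task and the passage of time act in every arm. The planned ANOVA does answer it. The plan therefore holds a suitable test next to a hypothesis and a power claim that describe a different quantity, and no sentence says which result counts as behavioural target engagement.

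Two things are at stake. An active arm could improve by d of at least 0.3 while the ANOVA shows no difference between arms, and the wording would let that be reported as support for the hypothesis. Also, a reader cannot tell what the 80% refers to, or how a study powered for d = 0.90 bears on a hypothesis set at d = 0.3.

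**Working it through.** **Inputs from the documents.** 60 participants (sections 5.1 and 10.1); three arms (section 4.1); d = 0.90 with 80% power and eta-squared 0.18 with 80% power (section 15.2); d = 0.3 (section 15.1).

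**Assumptions.** Equal allocation (60/3 = 20 per arm) and a two-sided 5% level; neither is stated for Aims 1 and 2. No attrition rate is given, so n per arm runs from 16 to 20. The value 16 is where the Aim 1 figure fits a three-group F test: noncentrality λ = N × 0.18/0.82 = 10.54 at N = 48 gives 80.9% power, against λ = 13.17 and 89.6% at N = 60.

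**Formulas.** With n per arm:
- paired t within one arm, d scaled by the SD of change: ncp = d√n, df = n − 1
- one active arm against sham: ncp = d√(n/2), df = 2n − 2
- three-arm ANOVA, one active arm (or both equally) differing from sham by d: λ = n × d² × 2/3, df = 2 and 3n − 3
- both active arms pooled against sham: ncp = d√(2n/3), df = 3n − 2

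**Step 1. Reproduce the stated 80% at d = 0.90.**

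| Reading | n = 16 | n = 19 | n = 20 |
|---|---|---|---|
| Paired, one arm | ncp 3.60: 91.9% | ncp 3.92: 96.0% | ncp 4.02: 96.8% |
| One active arm vs sham | ncp 2.55: 69.3% | ncp 2.77: 77.0% | ncp 2.85: 79.2% |
| Three-arm ANOVA | λ 8.64: 72.2% | λ 10.26: 80.3% | λ 10.80: 82.5% |
| Pooled active vs sham | ncp 2.94: 82.1% | ncp 3.20: 88.2% | ncp 3.29: 89.8% |

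A paired test on the SD of change reaches 80% with only 12 completers in an arm (81.0%). The label in the sentence therefore does not produce its figure on that scale. A between-arm comparison with 19 to 20 per arm does so closely. One caveat: if d is scaled by the raw-score SD, the paired effect becomes 0.90/√(2(1 − r)) for pre-post correlation r. That gives 80% at r = 0.07 (n = 20) or r = 0.28 (n = 16). The documents state neither that scale nor a correlation.

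**Step 2. Power at the hypothesised d = 0.3.**

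| Reading | n = 16 | n = 20 |
|---|---|---|
| One active arm vs sham | 13.0% | 15.2% |
| Three-arm ANOVA | 12.4% | 14.5% |
| Paired, one arm | 20.3% | 24.7% |

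**Step 3. Effect that gives 80% power.** Against sham: d = 0.91 at 20 per arm and 1.02 at 16. For the ANOVA: 0.87 and 0.98.

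**Step 4. Hypothesis 2.** With one omnibus test at 5% per circuit and independent circuits, the chance of at least one false positive is 1 − 0.95² = 9.75%. By simulation it falls to about 7% when the circuits correlate at 0.9.

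**The case against.** The best defence is that the planned analysis is already sham-controlled. The ANOVA includes sham, section 5.1 and Aim 3 both speak of comparison with sham, and in Aim 1 the protocol uses within-subject change for the quantity it then compares across arms. This largely stands. A reader might infer that the trial intends to declare success without reference to sham; the documents do not support that. Section 3.1 names a change endpoint, which is compatible with an ANOVA of change and is not itself an error. Hypothesis 1 shares the loose wording, but its model and its power sentence already name active versus sham. What remains is that the Aim 2 hypothesis and power sentence attach their effect sizes to the active arms alone.

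A reader might also infer that true Aim 2 power is a flat figure near 70%. That needs 16 completers per arm, which comes from one reading of Aim 1. Read as two equal arms, an eta-squared of 0.18 gives 80% at 19 per arm. Loss may also be smaller for the TST than for MRI: section 12.2 offers those who withdraw a last assessment without MRI, Table 1 lists the TST at follow-up, and assessments may be done remotely. Only a range is justified.

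Finally, a reader might want a rate at which CBIT alone would satisfy the Aim 2 wording. The documents give no CBIT effect on the TST, and they do not make an observed d of 0.3 a decision rule, so no such rate can be given.

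**Conclusion.** The mismatch is real and should be fixed. The Aim 2 hypothesis and power sentence describe within-arm improvement, while the test compares change between arms. As worded, the hypothesis could be met with no TMS effect.

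The 80% at d = 0.90 is not a paired within-arm figure on the SD-of-change scale (92-97%); it is most simply read as a between-arm figure at 19 to 20 per arm under the wrong label. If 16 to 20 per arm complete the TST, power at d = 0.90 is 69-79% for one active arm against sham, 72-83% for the ANOVA, and 82-90% for pooled active arms against sham. The hypothesised d = 0.3 has 12-25% power across the paired, single-arm-against-sham and ANOVA readings, and nothing reconciles it with 0.90. All of this rests on equal allocation, a two-sided 5% level and the assumed range of completers.

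The Hypothesis 2 point is secondary: about 7-10% false-positive risk over two circuits, with no rule, and with the status of connectivity in conflict between section 3.1 and Aim 1. The documents specify the circuit-level test only as an ANOVA; the LME described there is for SMA activation, and the SPU test is an added analysis of the whole CSTC.

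**What to change.** 1. Restate the Aim 2 hypothesis and power sentence as the active-minus-sham difference in pre-to-post TST change. Say that the planned ANOVA, followed by active-versus-sham contrasts, decides behavioural target engagement, and that within-arm changes are descriptive.
2. Recompute Aim 2 power for that comparison. State the allocation ratio, the alpha and sidedness, the TST attrition rate and the SD that scales d. The 80% benchmarks in step 3 of the working apply.
3. Reconcile d = 0.3 with the powered effect, for example by saying what role 0.3 plays if it is not the effect the trial can detect.
4. For Hypothesis 2, settle whether connectivity is primary or secondary, state that the group comparison of change is the test for each circuit, and apply Holm across SMA-DLS and SMA-M1 if success in either one remains the claim.

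**Cost.** A few sentences and no new data. Stated Aim 2 power may look less favourable. Requiring the ANOVA and then the contrast, with d = 0.90 in one arm, gives about 75% at 20 per arm and 64% at 16, against 80% and 70% for the contrast alone in the same calculation. Holm lowers Hypothesis 2 power at eta-squared 0.18, when only one circuit responds, from 90% to 83% (N = 60) or from 81% to 72% (N = 48), so by up to about 9 points.
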